4.2 Evaluable Patients

Patients will be deemed evaluable for hematologic response if they receive Metformin for at least one month in duration or if they receive Metformin for any duration of time and discontinue therapy for reasons related to study drug.

5 TREATMENT PLAN

5.1 Treatment Regimen

5.1.1 Pharmaceutical

Generic name: Metformin

Supply: Commercially available, generic

Route of administration: Oral

Pharmacology: Metformin is a biguanide derivative and is approved as an adjunct to diet and exercise to improve glycemic control in adults and children with type 2 diabetes mellitus

Product formulation: Metformin 500mg immediate release tablets and Riomet (Metformin HCl oral solution) 500mg/5mL liquid will be utilized for this study

Storage: Tablets should be stored at room temperature, 20-25°C, excursions permitted to 15-30°C; liquid should be stored at controlled room temperature 15-30°C (59-86°F)

5.1.2 Overview of Treatment Regimen

Patients may begin therapy on any day of the week. Each dose of Metformin will be recorded in a medication diary by patients \geq age 18, and by parents of patients $<$ age 18. The medication diary will be returned to clinic staff at the end of each month. Dose modifications are described in Section 7.2. Reported adverse events and potential risks are described in Section 7. No investigational or commercial agents or therapies other than Metformin may be administered with the intent to treat the participant's cytopenias. Participants may continue to receive Metformin for up to 6 months unless they satisfy the criteria for removal from protocol therapy (see Section 5.5).

To minimize the risk of gastrointestinal upset, patients will increase the dose of Metformin over 4 weeks as follows.

For patients \geq 10 years of age:

Initiation Phase:

Metformin will be initiated at a dose of 500mg/day, increased by 500mg/day once a week up to 2000mg/day.

Timepoint	Dose
Week 1	500mg qPM
Week 2	500mg BID
Week 3	500mg qAM, 1000mg qPM
Week 4 through end of treatment	1000mg BID

Maintenance phase: Patients will continue on the maximum dose of 1000mg BID or otherwise maximum tolerated dose for 6 months total duration.

For patients \geq 6 years of age and $<$ 10 years of age:

Initiation phase:

Metformin will be administered at a dose of 500mg/day and increased by 500mg/day once a week up to 1000mg/day.

Timepoint	Dose
Week 1	500mg qPM
Week 2 through end of treatment	500mg BID

Maintenance phase: Patients will continue on the maximum dose of 500mg BID or otherwise maximum tolerated dose for 6 months total duration.

Dose Modification:

For patients who have difficulty tolerating Metformin at any point during the initiation or maintenance phases due to gastrointestinal upset or other AEs specified in section 7, the dose will be decreased by 500mg/day until a tolerated dose is achieved.

Dose interruption:

Patients must hold Metformin if they are NPO for any reason, have a period of prolonged fast more than 8 hours, a critical illness requiring IV fluids, and/or a gastrointestinal illness. The medication will be held until patient resumes regular PO intake.

Patients must hold Metformin for 24 hours prior to imaging scans which require contrast, such as CT scans. Patients may resume Metformin 24 hours after the completion of the contrast administration.

Dose interruptions will typically occur for no more than 7 days and will be monitored.

5.2 Agent Administration

Metformin is administered orally with food either once or twice daily as specified per dose level.

Metformin is supplied as a 500mg pill and a 500mg/5mL liquid.

Metformin is to be taken with meals (± 30 minutes) to minimize GI upset. If a participant vomits a dose, the dose will not be repeated.

Each dose of Metformin will be recorded in a medication diary by a parent if patient age < 18 years of age, or by the patient if ≥ 18 years of age. The medication diary will be returned to clinic staff at the end of month.

5.3 Study Visit Procedures

A total of 12 visits will be required in this study. Some visits are in person at Boston Children's Hospital, and some visits will be conducted over the phone with parents if $<$ age 18 or with the patient if ≥ 18 years of age.

Visits 1 and 11 must be performed at the study site (Boston Children's Hospital). For patients

who are able to travel to Boston Children's Hospital for visit 6, pharmacokinetic studies will be performed. After initiation of study drug and prior to the end of therapy visit, subjects will be followed by their home physician or at Boston Children's Hospital and have blood work performed locally for interim visits as detailed below. The research team will contact the family for the interim phone calls as specified for visits 3, 4, 5, 7, 8, 9, 10, 12 to review drug diaries and adverse events and confirm laboratory assessments to be performed.

5.3.1 Visit 1: Baseline laboratory assessments – *BCH visit* (Day -28 to -1)

- Obtain informed consent
- Medical history
- Physical examination
- Lansky/Karnofsky Performance Status
- Height and weight
- Vital Signs
- Laboratory assessments: hematology (CBC with differential and reticulocyte count), chemistry (chem 10, LFTs), vitamin B12, G6PD, blood glucose, insulin level, oral glucose tolerance test, IGFBP-1, chromosomal breakage test, iron studies, hemoglobin electrophoresis
- Urinalysis
- Serum or urine pregnancy test
- Biomarker: bone marrow aspirate/biopsy
- Biomarker: aldehyde analyses
- Biomarker: buccal swab
- Distribution of drug diary

5.3.2 Visit 2: Initiation of therapy (Day 1)

- Drug administration: if the subject does not live locally and cannot pick up the study drug from BCH, drug will be shipped to the subject's home. Day 1 will be considered the day that the subject takes the study drug for the first time.

5.3.3 Visit 3 – *phone call* (Day 8 *+/- 3 days*)

- Drug diary review
- Adverse event assessment

5.3.4 Visit 4 – *phone call* (Day 15 *+/- 3 days*)

- Drug diary review
- Adverse event assessment

5.3.5 Visit 5 – *phone call* (Day 22 *+/- 3 days*)

- Drug diary review
- Adverse event assessment

5.3.6 Visit 6 – *phone call and local labs or BCH visit* (Day 29 *+/- 7 days*)

- Laboratory assessments: hematology (CBC with differential and reticulocyte count), chemistry (chem 10, LFTs), blood glucose, insulin level. Subjects able to travel to BCH for this visit will return to outpatient blood drawing at BCH and will also have pharmacokinetic assessments performed at this time. Subjects unable to travel to BCH for this visit will have their blood drawn at their primary clinician or an outside lab, and the report will be sent to BCH. An in-person study visit is not needed at this time point.
- Pharmacokinetic assessments: Will be performed for local patients at 0, 1, 2, 4, 6

hours post dose

- Drug diary review
- Adverse event assessment

5.3.7 Visit 7 – *phone call and local labs* (Day 57 *+- 7 days*)

- Laboratory assessments: hematology (CBC with differential and reticulocyte count)
- Drug diary review
- Adverse event assessment

5.3.8 Visit 8 – *phone call and local labs* (Day 85 *+- 7 days*)

- Laboratory assessments: hematology (CBC with differential and reticulocyte count), chemistry (chem 10, LFTs), blood glucose, insulin level
- Urinalysis
- Urine pregnancy test
- Drug diary review
- Adverse event assessment

5.3.9 Visit 9 – *phone call and local labs* (Day 113 *+- 7 days*)

- Laboratory assessments: hematology (CBC with differential and reticulocyte count)
- Drug diary review
- Adverse event assessment

5.3.10 Visit 10 – *phone call and local labs* (Day 141 *+- 7 days*)

- Laboratory assessments: hematology (CBC with differential and reticulocyte count)
- Drug diary review
- Adverse event assessment

5.3.11 Visit 11: End of study treatment – *BCH visit* (Day 169 *+- 14 days*)

- Physical examination
- Lansky/Karnofsky Performance Status
- Height and weight
- Vital Signs
- Laboratory assessments: hematology (CBC with differential and reticulocyte count), chemistry (chem 10, LFTs), vitamin B12, blood glucose, insulin level, oral glucose tolerance test, IGFBP-1, chromosomal breakage test, iron studies, hemoglobin electrophoresis
- Urinalysis
- Urine pregnancy test
- Biomarker: bone marrow aspirate/biopsy
- Biomarker: aldehyde analyses
- Biomarker: buccal swab
- Drug diary review
- Adverse event assessment

5.3.12 Visit 12 – *phone call and local labs* (Day 197 *+- 7 days*)

- Laboratory assessments: hematology (CBC with differential and reticulocyte count)
- Adverse event assessment

Additional labs may be performed as clinically indicated.

5.4 General Concomitant Medication and Supportive Care Guidelines

5.4.1 Concomitant Medications

5.4.1.1 No other medication targeting hematopoiesis will be used concurrently, including androgens or hematopoietic stimulating agents such as EPO, G-CSF, or TPO agonists. The use of furosemide is contraindicated.

5.4.1.2 The following medications should be used with caution:

- Cationic drugs that are eliminated by renal tubular excretion should be used with caution (amiloride, digoxin, morphine, procainamide, quinidine, quinine, ranitidine, triamterene, trimethoprim, and vancomycin).
- Other cationic transport-2 (OCT2)/multidrug and toxin extrusion (MATE) inhibitors include ranolazine, vandetanib, dolutegravir, and cimetidine.
- Carbonic anhydrase inhibitors, such as topiramate
- Nifedipine

5.4.1.3 Patients must not be on any anti-neoplastic agents during the duration of this study.

5.4.1.4 Appropriate antibiotics, blood products including transfusions, anti-emetics, fluids, electrolytes and general supportive care are to be used as clinically indicated.

5.5 Criteria for Taking a Participant Off Protocol Therapy

Duration of therapy will depend on individual response, evidence of disease progression, and tolerance. Treatment may continue for up to 6 months from study entry and completion of planned follow-up, or until one of the following criteria applies:

- Diagnosis of myelodysplastic syndrome or leukemia
- Worsening of cytopenias as defined by one of the following, sustained over 8 weeks in duration:
 - Increase in transfusion requirement by two-fold
 - Decrease in hemoglobin by $>1.5\text{g/dL}$ and absolute value $<10\text{g/dL}$
 - Platelet count $<50\%$ of baseline value and absolute value $<100\text{k}$
 - ANC $<50\%$ of baseline value and absolute value <1000
- Intercurrent illness that prevents further administration of treatment
- SAE or other toxicity that meets criteria for removal from protocol therapy (see Section 7)
- Participant demonstrates an inability or unwillingness to comply with the oral medication regimen and/or documentation requirements

- Found to be ineligible, including participants who have repeat organ function laboratory at the baseline assessment which no longer meet eligibility criteria.
- Participant decides to withdraw from the protocol therapy
- General or specific changes in the participant's condition render the participant unacceptable for further treatment in the judgment of the treating investigator
- Withdrawal of consent for treatment or treatment and data submission
- Death

The reason for taking a participant off study, and the date the participant was removed, must be documented in the case report form (CRF).

Participants will be removed from the protocol therapy when any of these criteria apply. The reason for removal from protocol therapy and the date the participant was removed must be documented in the case report form (CRF).

In the event of unusual or life-threatening complications, treating investigators must immediately notify the Overall PI.

5.6 Duration of Follow Up

Participants will be followed for one month after study treatment is complete or until death, whichever occurs first. Participants removed from protocol therapy for unacceptable adverse event(s) will be followed until resolution or stabilization of the adverse event.

5.7 Schedule of Assessments

Baseline disease assessments, such as bone marrow studies, must be performed within 28 days prior to starting study drug.

Study visits 2-5 should be within +/- 3 days of, visits 6-10 and 12 should be within +/- 7 days, and visit 11 should be performed within +/- 14 days of what is specified per protocol.

Visit Name	Screening									End of treatment	Follow up	
Visit number	1	2 ⁺	3	4	5	6	7	8	9	10	11	12

Day of cycle (+/-3 days unless otherwise indicated)	-28 to -1	1	8	15	2	29 (+/-7 days)	57 (+/-7 days)	85 (+/-7 days)	113 (+/-7 days)	141 (+/-7 days)	169 (+/-14 days)	197 (+/-7 days)
Obtain Informed Consent	X											
Demography	X											
Inclusion/exclusion criteria	X											
Relevant medical history/current medical conditions	X											
Diagnosis of Fanconi Anemia	X											
Prior therapies	X											
Concomitant medications	X											
Physical examination	X										X	
Lansky/Karnofsky Performance status	X										X	
Height	X										X	
Weight	X										X	
Vital signs	X										X	
Bloodwork	X					X	X	X	X	X	X	X
- Hematology (CBC with diff and retic)	X					X	X	X	X	X	X	X
- Chemistry (chem 10, LFTs)	X					X		X			X	
- Vitamin B12 level	X										X	
- G6PD	X											
- Blood glucose	X					X		X			X	
- Insulin level	X					X		X			X	
- Oral glucose tolerance test	X										X	
- IGFBP-1	X										X	
- Chromosomal breakage test	X										X	
- Iron studies (TIBC, serum iron, ferritin)	X										X	
- Aldehyde analyses	X										X	
- Hemoglobin electrophoresis	X										X	

Urinalysis (macroscopic)	X						X			X	
Serum or urine pregnancy test	X						X			X	
Drug dispensation		X									
Pharmacokinetic samples					X **						
Buccal swab sample for micronuclei assessment	X									X	
Bone marrow aspirate/biopsy	X									X	
- Aspirate for morphology	X									X	
- Biopsy	X									X	
- Karyotype	X									X	
- BMF/MDS FISH	X									X	
- Flow cytometry	X									X	
- CD34 HSPC cycling	X									X	
- Aldehyde analyses	X									X	
Drug diary/Drug administration							X				
Research team phone calls			X	X	X	X ***	X	X	X	X	X

+ Visit 2 is the day that the subject begins taking the study drug

** To be completed if study visit 6 occurs at BCH

*** To be completed if study visit 6 does not occur at BCH

6 HEMATOLOGIC RESPONSE CRITERIA

Hematologic improvement is based on modified MDS IWG criteria, which is listed below.²⁴
 Improvement in counts should be sustained for at least two months and demonstrated by at least 2 consecutive measurements to be considered a hematologic response

Hematologic improvement	Response Criteria (responses must be sustained over a minimum of 8 weeks in duration)		
Erythroid response (pretreatment, <10g/dL)	Hgb increase by $\geq 1.5\text{g/dL}$ for non-transfusion dependent patients	For patients who are transfusion dependent: Transfusion independence Only transfusions given for Hgb $\leq 8\text{g/dL}$ or for symptoms will be counted in the response evaluation	
Platelet response (pretreatment, <100k/uL)	If initially $<20\text{k/uL}$ to start, then must increase to	If initially $\geq 20\text{k/uL}$ to start, then must have an absolute	

	>20k/UL with an absolute increase of 100%	increase of >30k/UL
Neutrophil response (pretreatment <1000/uL)	If initially <500/uL to start, then must increase to >500/uL with an absolute increase of >250/uL	If initially ≥500/uL to start, then must have an absolute increase of >500/uL
Progression or relapse after HI*	At least one of the following: Decrease in ANC by >50% from baseline and absolute value <1000, platelet count decrease by >50% from baseline and absolute value <100k, reduction in Hgb by ≥1.5g/dL and absolute value <10g/dL, or doubling in transfusion requirement	

7 ADVERSE EVENTS: LIST AND REPORTING REQUIREMENTS

Principal Investigator will submit reports of unexpected SAEs and other unanticipated problems to the Institutional Review Board (IRB) at Boston Children's Hospital and the Medical Monitor.

All serious adverse events regardless of attribution relative to study will be reported for review on an expedited basis. Unanticipated Problems which are related or possible related to study participation and which are:

- 1) non-serious AEs but which are unexpected (in terms of unanticipated nature, frequency, or severity) and are thought to represent an increased risk of harm to study participants
- 2) events which are not AEs but which add risk to participants or others (e.g. breach of confidentiality) should be reported on an expedited basis.

- **Attribution** of the AE:

- Definite – The AE is *clearly related* to the study treatment.
- Probable – The AE is *likely related* to the study treatment.
- Possible – The AE *may be related* to the study treatment.
- Unlikely – The AE is *doubtfully related* to the study treatment.
- Unrelated – The AE is *clearly NOT related* to the study treatment.

- **Seriousness** of the AE:

An AE is to be classified as “serious” (SAE) if it meets any of the following criteria:

Death of Patient	An event that results in the death of a patient.
Life-Threatening	An event that, in the opinion of the investigator, would have resulted in immediate fatality if medical intervention had not been taken. This does not include an event that would have been fatal if it had occurred in a more severe form.
Hospitalization	An event that results in an admission to the hospital for any length of time. This does not include an emergency room visit or admission to an outpatient facility.
Prolongation of Hospitalization	An event that occurs while the study patient is hospitalized and prolongs the patient's hospital stay.

Congenital Anomaly	An anomaly detected at or after birth or any anomaly that result in fetal loss.
Persistent or Significant Disability/ Incapacity	An event that results in a condition that substantially interferes with the activities of daily living of a study patient. Disability is not intended to include experiences of relatively minor medical significance such as headache, nausea, vomiting, diarrhea, influenza, or accidental trauma (e.g., sprained ankle).
Important Medical Event Requiring Medical or Surgical Intervention to Prevent Serious Outcome	An important medical event that may not be immediately life-threatening or result in death or hospitalization, but based on medical judgment may jeopardize the patient and may require medical or surgical intervention to prevent any of the outcomes listed above (i.e. , death of patient, life-threatening, hospitalization, prolongation of hospitalization, congenital anomaly, or persistent or significant disability/incapacity). Examples of such events include allergic bronchospasm requiring intensive treatment in an emergency room or at home, blood dyscrasias or convulsions that do not result in inpatient hospitalization, or the development of drug dependency or drug abuse.

An AE that meets none of the above criteria is considered “non-serious”.

NOTE: Seriousness is independent of attribution or expectedness of the AE.

- **Expectedness** of the AE: In addition to term, grade, attribution, and seriousness, adverse events that have the potential to qualify for expedited reporting are to be designated as “expected” or “unexpected”. For the purposes of determining expectedness, all of the adverse events listed in Section 7.2 are to be considered expected.

7.1 Adverse Event Management

Toxicities will be assessed according to NCI’s CTCAE version 4.0.

Metformin is primarily associated with gastrointestinal side effects and if patients are not able to tolerate therapy based on these side effects, they will undergo a dose reduction. Management guidelines are listed below in the dose modification section 7.2. Metformin is rarely associated with lactic acidosis, in which case the drug will be discontinued and patients will receive appropriate clinical management.

Adverse events and toxicities will be captured both by planned laboratory studies at pre-specified timepoints (see study calendar) as well as by patient reporting. Patient interviews will be conducted weekly and drug diaries reviewed weekly during the initiation phase, and then monthly during the maintenance phase of treatment.

7.2 Dose modification

Gastrointestinal toxicities

Grade 1	Continue to follow treatment plan in section 5.1.2.
Grade 2	Maintain study agent at current dose. If

	resolves to grade 1 or less within 7 days, may increase Metformin dose as applicable. If does not resolve to grade 1 or less within 7 days, decrease to last tolerated dose level. If patient is on 500mg daily, then discontinue study treatment.
Grade 3	Decrease study treatment to last tolerated dose level. If toxicity does not resolve to grade 2 or less within 7 days, discontinue study treatment. If toxicity resolves to grade 2 or less within 7 days, may continue at lower dose level. Do not increase dose further.
Grade 4	Discontinue study treatment.

Renal toxicities

Estimated creatinine clearance <60ml/min	Hold study drug until creatinine clearance >60ml/min and at steady state, then may resume at last tolerated dose level.
Estimated creatinine clearance <30ml/min	Discontinue study treatment.

Metabolic toxicities

Symptomatic hypoglycemia Grade 1	Hold study drug until symptoms resolve to <grade 1, then may resume at last tolerated dose level if symptoms resolve within 7 days.
Hypoglycemia \geq Grade 2	Discontinue study treatment.
Acidosis \geq Grade 2	Discontinue study treatment.
Electrolyte abnormalities \geq Grade 3	Provide supportive care, hold study treatment until <grade 1. May resume at last tolerated dose or discontinue per investigator discretion.

Hematologic toxicities

Grade 1 or 2	Continue to follow treatment plan in section 5.1.2.
Grade 3	Maintain study agent at current dose. Transfuse if clinically indicated.
Grade 4	If patients meet criteria for worsening of cytopenias requiring removal of patient from study as defined in Section 5.5, then discontinue study drug. Otherwise, maintain study agent at current dose and transfuse if clinically indicated.

Other non-hematologic toxicities considered to be related to Metformin

Grade 1	Continue to follow treatment plan in section 5.1.2.
---------	---

Grade 2	Maintain study agent at current dose. If resolves to grade 1 or less within 7 days, may increase Metformin dose as applicable. If patient is on 500mg daily, then discontinue study drug.
Grade 3	Decrease study treatment to last tolerated dose level. If patient is on 500mg daily, then discontinue study drug. If toxicity does not resolve to grade 2 or less within 7 days, discontinue study treatment. If toxicity resolves to grade 2 or less within 7 days, may continue at lower dose level. Do not increase dose further.
Grade 4	Discontinue study treatment.

8 DATA REPORTING / REGULATORY REQUIREMENTS

Adverse event lists, guidelines, and instructions for AE reporting can be found in Section 7.

8.1 Safety Monitoring

The medical monitor will review and monitor toxicity and accrual data from this study. The medical monitor will be a clinical specialist with experience in hematology and who have no direct relationship with the study. Information that raises any questions about participant safety will be addressed with the Overall PI and study team.

The medical monitor will review this protocol up to four times per year or more often if required to review toxicity and accrual data. Information to be provided to the committee may include: up-to-date participant accrual; all grade 2 or higher unexpected adverse events that have been reported; summary of all deaths occurring within 30 days of intervention; any response information; audit results; and a summary provided by the study team. Other information (e.g. scans, laboratory values) will be provided upon request.

8.2 Stopping Rules Data

The study will be monitored to ensure that treatment related serious adverse events do not exceed the anticipated rate based on previous clinical studies. The study will be paused to accrual for review by the medical monitor, and may be terminated early if there are any grade V toxicities considered to be probably or definitely related to Metformin. If there are $\geq 3/24$ patients with non-hematologic non-GI grade IV events that are attributed to be at least possibly related to Metformin which are observed during any point in the study, the study may be paused for accrual for evaluation by the medical monitor. Management for grade IV toxicities will be provided with guidance regarding holding medication and monitoring for resolution of toxicities (Section 7.2).

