9.3 Interim Analysis

Given that this is a pilot study of 24 patients, no interim analysis is planned.

The study accrual may be suspended if there are $\geq 3/24$ patients with non-hematologic non-GI grade IV events that are attributed to be at least possibly related to Metformin which are observed during any point in the study. The probability of observing 3 or more events among 24 subjects is equal to 0.89 if the observed rate is 20% and 0.12 if the observed rate is 5%.”

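### A death rated only possibly related to Metformin meets neither accrual-pause rule in section 8.2, because the rules use different attribution tests and the tally names grade IV only

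*Combined protocol and SAP*

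**What the plan says.** Section 8.2 contains two rules for pausing accrual.

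- **Grade V rule.** One event is enough. The trigger is "any grade V toxicities considered to be probably or definitely related to Metformin". The consequence is firm as to the pause and optional as to termination: "The study will be paused to accrual for review by the medical monitor, and may be terminated early".
- **Grade IV tally.** The trigger is at least 3 of 24 "patients with non-hematologic non-GI grade IV events that are attributed to be at least possibly related to Metformin", at any time in the study. The consequence is optional: "the study may be paused for accrual for evaluation by the medical monitor".

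Section 9.3 repeats the tally ("The study accrual may be suspended if there are" at least 3 of 24 such patients) with the same attribution test, "attributed to be at least possibly related to Metformin". It gives the chance of reaching the tally as "equal to 0.89 if the observed rate is 20% and 0.12 if the observed rate is 5" per cent. It does not mention the grade V rule.

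Section 7 defines five attribution ratings: Definite, Probable, Possible, Unlikely and Unrelated. It also has every serious adverse event, death included, reported for expedited review whatever its attribution. Section 8.1 says that the material sent to the medical monitor may include a "summary of all deaths occurring within 30 days of intervention". Reviews take place up to four times a year, or more often if needed.

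**The concern.** The most severe outcome carries the stricter attribution test. A death rated Possible fails the grade V rule on attribution. It also falls outside the tally, which names grade IV and does not say grade IV or higher. No reason is given for the difference. The looser test, at least possibly related, appears in the tally in 8.2, in its repeat in 9.3, and as one of the two bases for reporting toxicity in 9.7.

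The rating Possible is likely to be used here. The trial is open-label with a single arm, and section 2.1 describes a population at high risk of aplastic anemia, MDS, AML and solid tumors. With no control group and several competing causes of death, an investigator may find it hard to go beyond Possible. At stake is whether the written rules would stop enrollment while such a death is reviewed, or whether that would rest on judgment alone.

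**Working it through.** **Step 1. Reproduce the plan's own figures.** Inputs are n = 24 and a threshold of 3 patients (8.2 and 9.3), with the rates in 9.3 read as true per-patient rates. The formula is P(X ≥ 3) = 1 − [(1−p)^24 + 24·p·(1−p)^23 + 276·p²·(1−p)^22].

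- p = 0.05: 1 − (0.2920 + 0.3688 + 0.2232) = 0.116, which rounds to the stated 0.12.
- p = 0.20: 1 − (0.0047 + 0.0283 + 0.0815) = 0.885, which rounds to the stated 0.89.

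Both figures are right for the grade IV tally. No operating characteristics are given for the grade V rule.

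**Step 2. Put a death rated Possible through each rule.**

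| | Grade V rule | Grade IV tally |
|---|---|---|
| Events needed | 1 | 3 patients of 24 |
| Grade | V | IV |
| Organ exclusions | none | hematologic and GI excluded |
| Attribution | Probable or Definite | Possible or higher |
| Pause | mandatory | discretionary |
| Does a death rated Possible count? | No: fails on attribution | No: not a grade IV event |

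If the same patient had a qualifying grade IV event recorded before death, that event counts as one of the three. The death itself does not.

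**Step 3. Look for a pause elsewhere.** Section 5.5 requires immediate notice to the Overall PI of unusual or life-threatening complications. Section 7 requires expedited reporting. Section 8.1 provides for review by the medical monitor and for safety questions to be taken up with the Overall PI and study team. None of these provisions attaches an accrual pause.

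**Step 4. Size.** The documents give no rate of possibly related death, so the rates below are assumptions. The chance of at least one among 24 is 1 − (1−p)^24. The last column is the chance that such deaths alone would reach three patients if the tally read grade IV or higher. It assumes that every one of them is non-hematologic and non-GI.

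| Assumed true rate | At least 1 of 24 | At least 3 of 24 |
|---|---|---|
| 0.5% | 1 − 0.995^24 = 0.113 | 0.0002 |
| 1% | 1 − 0.99^24 = 0.214 | 0.0017 |
| 2% | 1 − 0.98^24 = 0.384 | 0.012 |
| 5% | 1 − 0.95^24 = 0.708 | 0.116 |

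As worded, neither rule is triggered by these deaths at any of these rates. The last column shows that extending the tally to grade V would seldom matter by itself. The attribution wording is the substantive part.

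**The case against.** The strongest defence is that the two rules are different instruments. The grade V rule acts on one event and forces a pause. The tally needs three patients, excludes hematologic and GI events, and only permits a pause. A stricter attribution test on a mandatory single-event trigger is a recognisable trade-off in patients with substantial background risk, some of whom may enroll with very severe aplastic anemia if they are not eligible for transplant (3.2.2). This stands as a possible rationale, but the protocol does not state it. It also does not explain why the tally should omit grade V.

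A reader might infer more than the text supports, in four ways.

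- *That one possibly related grade IV event pauses accrual while a possibly related death does not.* Three patients are needed, and even then the pause is optional.
- *That such a death would go unreviewed until a periodic meeting.* Section 7 requires expedited reporting regardless of attribution, and 8.1 allows reviews beyond four a year. One limit remains: the sentence in section 7 that names the medical monitor as recipient covers unexpected serious events, and the sentence on expedited reporting names no recipient.
- *That the probabilities in 9.3 are wrong or claim to cover deaths.* They reproduce, and they describe only the tally set out just before them.
- *That the chance of an uncovered death is as high as 71%.* That figure needs an assumed 5% rate. Section 2.2 describes low toxicity and no lactic acidosis in 70,490 patient-years, which gives no reason to prefer the top of the range.

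**Conclusion.** The point holds as a gap in the formal rules: a death rated Possible triggers neither pause rule in 8.2. This follows from the wording and the ratings in section 7, and it does not depend on any rate. Its practical size does depend on one. Over assumed rates of 0.5% to 5%, the chance that at least one such death occurs among 24 patients runs from 11% to 71%. These figures treat patients as independent with a common rate.

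What is missing is a written pause. Reporting and discretionary review are in place, and a discretionary pause remains open to the study team. The severity is minor. The point is worth acting on because the repair is short and concerns participant safety.

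**What to change.** Reconcile the two rules in 8.2, and the repeat of the tally in 9.3, as follows.

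- Align the attribution wording so that a grade V event does not face a stricter test than a grade IV event, or state the reason if the difference is intended. The sponsor and medical monitor choose the threshold.
- Word the 3-of-24 tally to count qualifying events of grade IV or higher, in both sections. The 0.12 and 0.89 can stay, read as the chance of reaching that tally at true rates of 5% and 20% for the events it counts.

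The cost is a sentence or two in 8.2 and a matching change in 9.3. The downside is an occasional extra accrual pause for a death later judged unrelated. If the sponsor applied the looser test to the single-event grade V rule, the chance of at least one pause from possibly related deaths would be the at-least-one column above, under the same assumed rates. Sample size and the primary analysis are unaffected.
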